	26	600:00	18:00	Ambulatory visit ¹¹ , admin. 10 mg donepezil		x ⁸					x ^{2,7}	
	27	624:00	18:00	Ambulatory visit ¹¹ , admin. 10 mg donepezil		x ⁸					x ^{2,7}	
	28	648:00	18:00	Ambulatory visit ¹¹ , admin. 10 mg donepezil		x ⁸					x ^{2,7}	
29	672:00	18:00	Ambulatory visit ¹¹	x ¹⁰	x ⁸			x ²	x ²	x ^{2,7}		
4	44-49	n.a.	n.a.	End of trial examination ⁴	x ¹⁰			x ^{12,13}	x	x	x	

1. Screening includes subject information, informed consent, physical examination including neurological assessment, check of vital signs, visual tests, ECG, safety laboratory (including drug screening, alcohol breath test, urine pregnancy testing in females, and faecal occult blood test), demographics (including determination of body height and weight, smoking status and alcohol history), relevant medical history, concomitant therapy and review of inclusion/exclusion criteria.
2. The time is approximate; the procedure is to be performed and completed within 2 h prior to drug administration.
3. If several actions are indicated at the same time point, the intake of meals will be the last action.
4. End of trial examination includes physical examination including neurological assessment, vital signs, visual tests, ECG, safety laboratory, urine pregnancy testing in females, recording of AEs and concomitant therapies, faecal occult blood test.
5. Including urine drug screening and alcohol breath test and urine pregnancy testing in females
6. AEs and concomitant therapies will be recorded throughout the trial, but will be specifically asked for at the time points indicated in the [Flow Chart](#) above.
7. Includes questioning for 'restrictions'

8. Pre-dose PK, i.e. within 10 min prior to the next drug administration
9. Safety laboratory to be taken within 3 days prior to first trial drug administration of Visit 2 and 3. All results must be available and be checked by the investigator or his/her designee before trial drug administration. For Visit 3, the safety laboratory of day 8, Visit 2 will be used.
10. Includes immunochemical faecal occult blood (iFOB) test
11. Discharge after confirmation of fitness by the investigator/designee
12. Neurological assessment (i.e. Romberg and Unterberger test, assessment of gait, further tests as needed) to be performed at the time points mentioned in the [Flow Chart](#) above and at any times CNS adverse events are reported

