1.2.2 Donepezil

Donepezil is a specific and reversible inhibitor of acetylcholinesterase, the predominant cholinesterase in the brain. Current theories on the pathogenesis of the cognitive signs and symptoms of Alzheimer's disease attribute some of them to a deficiency of cholinergic neurotransmission [R15-4794]. Donepezil is indicated for the symptomatic treatment of mild to moderate dementia of the Alzheimer's type and commonly used in this patient population [R18-3913].

In mild to moderate AD the dosing recommendation is a daily dose of 5 mg q.d. which might be increased to a maximum dose of 10 mg q.d.. For tolerability reasons, it is recommended to administer donepezil in the evening and to use an up-titration scheme starting with 5 mg donepezil q.d. and increasing to 10 mg q.d. if needed and well tolerated.

Maximum plasma levels after administration of 10 mg donepezil are reached approximately 3 - 4 hours after oral administration [R15-4794, R18-3913].

The terminal disposition half-life is approximately 70 hours. Following multiple dose administration, steady state is reached within ~3 weeks. Donepezil is mainly excreted (57%) in the urine, both intact (17%) and metabolized, and also via faeces (14.5%). It is extensively metabolized to four major metabolites, of which one, 6-O-Desmethyl-Donepezil has a comparable activity to donepezil, and a number of minor metabolites, of which not all have been identified [R18-3913].

In vitro studies have shown that CYP3A4 and to a minor extent CYP2D6 are involved in the metabolism of donepezil. In a study in healthy volunteers, ketoconazole increased mean donepezil concentrations by about 30 %. In patients with mild – moderate hepatic impairment steady state exposures of donepezil were increased (AUC up to ~ 48%, C_{max} up to ~39%) [R18-3913].

Enzyme inducers such as rifampicin, phenytoin, carbamazepine and alcohol may reduce the levels of donepezil [R15-4794].

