3.3.2 Inclusion criteria

Subjects will only be included in the trial if they meet the following criteria:

1. Healthy male or female subjects according to the assessment of the investigator, as based on a complete medical history including a physical examination, vital signs (BP, PR), 12-lead ECG, and clinical laboratory tests
2. Age of 18 to 50 years (inclusive)
3. BMI of 18.5 to 29.9 kg/m² (inclusive)
4. Signed and dated written informed consent prior to admission to the study, in accordance with GCP and local legislation
5. Male subjects, or female subjects who meet any of the following criteria from the first administration of trial medication until 30 days after trial completion:
 - Use of adequate contraception that does not contain hormones, i.e. non-hormonal intrauterine device *plus* condom
 - Sexually abstinent
 - A vasectomised sexual partner (vasectomy at least 1 year prior to enrolment)
 - Surgically sterilised (including hysterectomy)
 - Postmenopausal, defined as at least 1 year of spontaneous amenorrhea (in questionable cases a blood sample with levels of FSH above 40 U/L and estradiol below 30 ng/L is confirmatory)

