3.3.3 Exclusion criteria

Subjects will not be allowed to participate, if any of the following general criteria apply:

1. Any finding in the medical examination (including BP, PR or ECG) deviating from normal and assessed as clinically relevant by the investigator
2. Repeated measurement of systolic blood pressure outside the range of 90 to 140 mmHg, diastolic blood pressure outside the range of 50 to 90 mmHg, or pulse rate outside the range of 50 to 90 bpm

3. Any laboratory value outside the reference range that the investigator considers to be of clinical relevance
4. Any evidence of a concomitant disease assessed as clinically relevant by the investigator
5. Gastrointestinal, hepatic, renal, respiratory, cardiovascular, metabolic, immunological or hormonal disorders
6. Cholecystectomy or other surgery of the gastrointestinal tract that could interfere with the pharmacokinetics of the trial medication (except appendectomy or simple hernia repair)
7. Diseases of the central nervous system (including but not limited to any kind of seizures or stroke), and other relevant neurological or psychiatric disorders
8. History of relevant orthostatic hypotension, fainting spells, or blackouts
9. Chronic or relevant acute infections
10. History of relevant allergy or hypersensitivity (including allergy to the trial medication or its excipients)
11. Use of drugs within 30 days of planned administration of trial medication that might reasonably influence the results of the trial (including drugs that cause QT/QTc interval prolongation)
12. Intake of an investigational drug in another clinical trial within 60 days of planned administration of investigational drug in the current trial, or concurrent participation in another clinical trial in which investigational drug is administered
13. Smoker (more than 10 cigarettes or 3 cigars or 3 pipes per day)
14. Inability to refrain from smoking on specified trial days
15. Alcohol abuse (consumption of more than 20 g per day for females and 30 g per day for males)
16. Drug abuse or positive drug screening
17. Blood donation of more than 100 mL within 30 days of planned administration of trial medication or intended blood donation during the trial
18. Intention to perform excessive physical activities within one week prior to the administration of trial medication or during the trial
19. Inability to comply with the dietary regimen of the trial site

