Alcoholic beverages, grapefruits, Seville oranges (sour or bitter oranges) and their juices, and dietary supplements and products including St. John's wort (*Hypericum perforatum*) are not permitted starting 7 days before the first administration of trial medication until after the last PK sample of each study period is collected.

Smoking is not allowed during in-house confinement at the trial site.

Methylxanthine-containing drinks or foods (such as coffee, tea, cola, energy drinks, and chocolate) are not allowed from 24 h before until 24 h after each administration of trial medication.

Excessive physical activity (such as competitive sport) should be avoided starting 7 days before the first administration of trial medication until the end of trial examination.

Direct exposure to the sun or exposure to solarium radiation should be avoided during the entire study.

If female subjects of child-bearing potential are included in the trial, adequate contraception is to be maintained throughout the course of the trial (see [Section 3.3.2](#) for the definition of adequate measures). Hormonal contraception is not allowed.

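### Screening and consent may fall as late as Day -1, after the 7-day pre-dose restrictions have already begun, in both parts

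*Protocol*

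**What the plan says.** **Timing of consent.** The Flow Chart for each part places the screening visit on Days -21 to -1. Footnote 1 in each reads "Screening includes subject information, informed consent, physical examination including neurological assessment", so consent may be given at that visit. Inclusion criterion 4 (Protocol 3.3.2) asks for "Signed and dated written informed consent prior to admission to the study" and sets no minimum interval before dosing.

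**Timing of the restrictions.** Under Protocol 4.2.2.2, alcoholic drinks, grapefruit, Seville oranges and supplements including St. John's wort "are not permitted starting 7 days before the first administration of trial medication". The same sentence carries the ban through to the last PK sample of each period. Excessive physical activity is to be avoided from the same starting point.

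**Entry criteria that touch on these items (Protocol 3.3.3).**
- Criterion 11: "Use of drugs within 30 days of planned administration of trial medication that might reasonably influence the results of the trial".
- Criterion 15: habitual alcohol intake above 20 g per day (females) or 30 g per day (males).
- Criterion 18: "Intention to perform excessive physical activities within one week prior to the administration of trial medication or during the trial".
- Criterion 19: "Inability to comply with the dietary regimen of the trial site".

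**Checks before the reference dose.** Flow Chart footnote 7 (questioning about restrictions) is marked on Day 1 of Visit 2, at -10:00 in Part 1 and -02:00 in Part 2. Footnote 15 gives an alcohol breath test at admission to Visit 2 in both parts.

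**Consequences.** Protocol 4.3 lets the site remove a subject who breaks trial restrictions but does not require it. SAP Table 6.2: 1 lists non-compliance, prohibited medication and improper washout as possible grounds for exclusion from the pharmacokinetic set (PKS), decided no later than the Report Planning Meeting.

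**The concern.** A subject who consents on Day -3 cannot have been told of a restriction that began on Day -7. That subject can meet every entry criterion and already be in breach of Section 4.2.2.2.

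The restrictions are there to protect the PK comparison. Protocol 1.3 says that both drugs are metabolised by CYP3A4 and calls BI 425809 a sensitive substrate. Section 1.2.2 adds: "Enzyme inducers such as rifampicin, phenytoin, carbamazepine and alcohol may reduce the levels of donepezil".

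The design has little defence against an effect carried in from before the study. Each part has one fixed sequence with the reference treatment first (Protocol 4.1.4), and the model contains only subject and treatment (Protocol 7.3.1, SAP 7.4.1). A period term could not be added, because period and treatment coincide. Section 3.2 relies on nonspecific time effects not being expected. A pre-study enzyme effect that wanes between the two doses would be read as part of the treatment effect. In Part 2, waning induction would lower the reference exposure, raise test/reference, and partly hide the fall in donepezil that Section 1.4 considers possible. Residual inhibition would act in the opposite direction.

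**Working it through.** **1. Calendar check.** Inputs: screening on Days -21 to -1 (both Flow Charts), and restrictions from 7 days before first dose (4.2.2.2). First dose is on Day 1 and there is no Day 0, so 7 days before is Day -7.

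For screening on Day -d with d < 7, the restricted days before consent number 7 - d.

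| Screening day | Restricted days before consent |
|---|---|
| -21 to -7 | 0 |
| -6 | 1 |
| -5 | 2 |
| -4 | 3 |
| -3 | 4 |
| -2 | 5 |
| -1 | 6 |

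Affected share of the permitted window: 6/21 = 28.6%. This is a share of calendar days. The documents do not say how screening visits will be spread over them.

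**2. What the existing checks reach.**

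| Item | Entry criterion | Pre-dose check |
|---|---|---|
| Grapefruit, Seville orange | None looks back; 19 looks forward | Restrictions question |
| Moderate alcohol | None below the limits in 15 | Restrictions question; breath test (recent drinking only) |
| St. John's wort | 11, if a supplement counts as a drug | Restrictions question; review of concomitant therapy |
| Excessive activity | 18, worded as an intention | Restrictions question |

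No criterion gives a 7-day look-back for grapefruit, Seville orange or moderate alcohol. The pre-dose checks can find a breach but cannot prevent one.

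**3. Size if a breach stays in the analysis.** With n complete pairs, if one subject's test/reference ratio is multiplied by a factor r, the geometric mean ratio is multiplied by r^(1/n): r^(1/18) in Part 1 and r^(1/14) in Part 2. The documents give no value of r for grapefruit, moderate alcohol or St. John's wort taken in the week before dosing, and no number of likely breaches, so no figure follows.

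**4. Size if the subject is excluded instead.** The 90% CI half-width on the log scale is proportional to t(0.95; n-1)/√n when the residual variance is unchanged.
- Part 1, from 18 to 17: (1.7459/√17)/(1.7396/√18) = 0.4234/0.4100 = 1.033.
- Part 2, from 14 to 13: (1.7823/√13)/(1.7709/√14) = 0.4943/0.4733 = 1.044.

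Losing one subject widens the interval by about 3% in Part 1 and about 4% in Part 2.

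**The case against.** The strongest reply is that the plan already catches these cases. Subjects are asked about restrictions before the reference dose and breath-tested at admission, and a further contact on Days -3 to -1 covers concomitant therapy. Under Protocol 4.1.3 a reserve subject can replace anyone who fails the trial's requirements before dosing. A breach found later can lead to exclusion from the PKS. The trial sets no acceptance range (Protocol 7.2), so no formal conclusion turns on a small shift. Most of this stands, and it is why the point is minor. What remains is that these safeguards act after the event, removal is optional, and the breach comes from the protocol's own calendar.

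Three stronger readings are tempting, and the documents do not support them.

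- *That nothing at entry checks these items.* Criterion 11 can reasonably be read to include St. John's wort, criterion 15 covers heavy drinking, and the pre-dose questioning covers the whole list.
- *That the bias can be sized by modelling an inducer stopped 7 days before dosing.* That describes a subject who complied with the ban. It asks whether 7 days is long enough, which is a different question, and it needs inputs that the documents do not give.
- *That the ethics committee has already objected to this.* Protocol Section 11.1 records a concern about a contraception period that began before consent. That period was removed because it was needed only for oral contraceptives. The similarity is fair to note, but no objection to the diet restrictions is recorded.

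**Conclusion.** The timing conflict is real in both parts: on 6 of the 21 permitted screening days, the restrictions precede consent by 1 to 6 days. This follows from the stated windows alone.

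The effect on the results is probably small. It requires a late-screened subject, relevant intake in the uncovered days, an effect that lasts until the reference dose, and a breach that is missed or tolerated on Day 1. A single such subject is then diluted by the exponent 1/18 or 1/14. The bias itself cannot be computed from the documents. The alternative, loss of one subject from the PKS, costs about 3% (Part 1) or 4% (Part 2) in interval width, assuming full enrolment, complete pairs and no replacement.

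Severity: minor. It is worth correcting because the correction is nearly free and the fixed sequence leaves no way to adjust for the effect in the analysis.

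**What to change.** 1. **Close the screening window before the restrictions start.** In both Flow Charts, change the screening entry to, for example, Days -21 to -8. Alternatively, keep the window and require consent and documented notice of the Section 4.2.2.2 restrictions no later than Day -7. The safety laboratory contact on Days -3 to -1 is unaffected.

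   Cost: two Flow Chart entries or one added sentence. Late replacements could no longer be screened in the last week, but the reserve subjects in Section 4.1.3, who are screened in advance, largely cover that need.

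2. **Reconcile the two windows for St. John's wort.** Criterion 11 (30 days, drugs) and Section 4.2.2.2 (7 days, supplements) can both be read as applying. The sponsor should state which governs pre-study use. The entry in Section 4.2.2.2 should stay in place, because the same sentence carries the explicit on-study ban; without it only the general CYP3A4 inhibitor and inducer rule in Section 4.2.2.1 would remain.

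   Cost: one clarifying phrase.

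Each change can be made without the other.

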4.3 TREATMENT COMPLIANCE

Compliance will be assured by administration of all trial medication in the study centre under supervision of the investigating physician or a designee. The measured plasma concentrations of trial medication will provide additional confirmation of compliance.

Subjects who are non-compliant (for instance, who do not appear for scheduled visits or violate trial restrictions) may be removed from the trial and the CRF will be completed accordingly (for further procedures, please see [Section 3.3.4.1](#)).

5. ASSESSMENTS

5.1 ASSESSMENT OF EFFICACY

Not applicable.

5.2 ASSESSMENT OF SAFETY

5.2.1 Physical examination

At the screening visit, the medical examination will include documentation of subject information, informed consent, demographics including height and body weight, smoking and alcohol history, relevant medical history and concomitant therapy, review of inclusion and exclusion criteria, visual tests, C-SSRS assessment (only for Part 2), review of vital signs (BP, PR), 12-lead ECG, laboratory tests, and a physical examination (including a neurological examination consisting of Romberg and Unterberger test, assessment of gait, further tests as needed). At the end of trial examination, it will include review of vital signs, 12-lead ECG, laboratory tests, C-SSRS assessment, visual tests and a physical examination with a neurological assessment (i.e. Romberg and Unterberger test, assessment of gait, further tests as needed). During the treatment period neurological examination (i.e. Romberg and Unterberger test, assessment of gait, further tests as needed) will be performed at the time points indicated in the [Flow Chart](#). In addition, neurological examinations are to be performed at any times CNS adverse events are reported. The occurrence of headache, however, does not require the performance of neurological assessments (except upon discretion of the investigator). The reason for this is that headaches are in most cases unspecific symptoms without clear causative CNS involvement that occur frequently in clinical trials in healthy volunteers. Abnormal findings in the neurological and physical examination will be reported as AEs

5.2.2 Vital signs

Systolic and diastolic blood pressures (BP) as well as pulse rate (PR) will be measured by a blood pressure monitor (Dinamap, GE Medical Systems, Freiburg, Germany) at the times indicated in the [Flow Chart](#), after subjects have rested for at least 5 min in a supine position. All recordings should be made using the same type of blood pressure recording instrument on the same arm if possible.

5.2.3 Visual tests

Visual tests will be performed at screening, EOT and any time the subject reports visual adverse events or if it is deemed necessary by the investigator or designee.

5.2.3.1 Color discrimination test

Color vision will be tested using the Ishihara test for color deficiency.

The test consists of a number of colored plates, called Ishihara plates, each of which contains a circle of dots appearing randomized in color and size. Within the pattern are dots which form a number visible to those with normal color vision and invisible, or difficult to see, for those with a color vision deficiency.

Examination of color vision will be carried out at the times indicated in the [Flow Chart](#) and any time the subject reports visual adverse events or if it is deemed necessary by the investigator or designee.

Two plates will be randomly selected for each time point as well as a plate with a positive (the plate number must be recognized by all subjects) and a negative control (the plate number should not be recognized by any subject).

Subjects will be instructed to recognize and report the numbers seen on the plates. Test results will be reviewed by investigator or his/her designee for correctness.

All test results will be documented in the source documents and entered in eCRF. Any abnormal findings detected in this test during the screening examination will lead to the exclusion of the subject. Any deterioration occurring during the study will be documented as an AE and an additional ophthalmologic examination should be considered.

5.2.3.2 Visual acuity test (near visual acuity)

Near vision cards (e.g. Jaeger Eye Chart) will be used to measure visual acuity. The smallest line that a subject can read at a distance of 35 centimeter will be recorded.

If the subject uses glasses, then the test should be performed using them.

Visual acuity testing will be carried out at the times indicated in the [Flow Chart](#) and any time the subject reports visual adverse events or if it is deemed necessary by the investigator or designee.

All test results will be documented in the source documents and entered in eCRF.

Tests results will be reviewed by investigator or his/her designee for correctness and deteriorations from the baseline will be documented as an AE (narratives will be written).

The test results will be documented, and during the course of the study, each post-dose result obtained in a particular subject will be compared to the baseline result.

5.2.3.3 Amsler grid test

The Amsler grid is a grid of horizontal and vertical lines used to monitor a person's central visual field. It is a diagnostic tool that aids in the detection of visual disturbances caused by changes in the retina, particularly the macula (e.g. macular degeneration, epiretinal membrane), as well as the optic nerve and the visual pathway to the brain.

If the subject uses glasses, then the test should be performed using them. Subjects should hold the Grid at a normal reading distance about 35 cm away from the face using only one eye (another eye closed) and look at the dot in the center of the grid. If any of the lines in the grid look distorted, blurry, or missing, this will be documented in the source documents as AE (narratives will be written).

Any abnormal findings detected in this test during the screening examination will lead to the exclusion of the subject. Any deterioration that occurred during the study will be documented as an AE and an additional ophthalmologic examination should be considered.

All test results will be documented in the source documents and entered in eCRF.

